7.2.1 Analyses of Primary Endpoint

7.2.1.1 Overall Response Rate

ORR will be derived from best overall response (BOR), which is defined as the best time point response that a subject achieves during the course of the study, with the response ranked according to the following order (from best to worst): CR>CRi>PR>PRwL>SD>PD (CRi applies to CLL only).

The estimated ORR (percent of subjects with a BOR of CR, CRi, PR or PRwL) and a 2-sided 95% CI will be provided. The 95% CI will be calculated using exact binomial method. Number and percent of subjects with BOR in each of the response categories (CR, CRi, PR, PRwL, SD, PD) will also be presented. All subjects in the analysis set will be included in the denominator in the calculation of the percentage for each response category or ORR.

Analysis of ORR using the PP analysis set will be provided as a sensitivity analysis.

Subgroup analyses will be performed for ORR using the subgroups specified in [Section 6.5](#).

7.2.2 Analyses of Secondary Efficacy Endpoints

The analysis of secondary efficacy endpoint, Duration of Response (DOR) and Progression Free Survival (PFS), will be descriptive only.

7.2.2.1 Duration of Response (DOR)

DOR will be presented using the Kaplan-Meier method based on all treated subjects with a documentation of response (i.e., CR, CRi, PR, or PRwL) as determined by investigator assessment. The censoring rule will be the specified in Appendix A. The Kaplan-Meier estimates of survival curves and number of subjects with events, types of events (progression or death before progression), number of subjects censored, number of subjects for each reason of censoring, estimates and 95% confidence intervals for the 25th percentile, median, and 75th percentile for DOR will be presented (if estimable).

Analysis of DOR using the PP analysis set will be provided as a sensitivity analysis.

7.2.2.2 Analyses of PFS

PFS will be presented using the Kaplan-Meier method based on all treated subjects with a documentation of response (i.e., CR, CRi, PR, or PRwL) as determined by investigator assessment. The censoring rule will be the specified in Appendix A. The Kaplan-Meier estimates of survival curves and number of subjects with events, types of events (progression or death before progression), number of subjects censored, number of subjects for each reason of censoring, estimates and 95% confidence intervals for the 25th percentile, median, and 75th percentile for PFS will be presented (if estimable).

PFS will be plotted using the Kaplan-Meier method. The plot will include the number of subjects at risk over time.

Analysis of PFS using the PP analysis set will be provided as a sensitivity analysis.

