9.2 ANALYSIS SETS

All subjects who received at least one dose of study drug in this extension study will be included in the All-Treated (AT) Analysis Set. This analysis set will be the primary analysis set for all efficacy and safety endpoints.

Additional analysis sets may be defined in the SAP.

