9.4 EFFICACY ANALYSES

ORR, DOR and PFS will be based on response and progression statuses as determined by investigators according to the IWCLL Response Criteria or revised IWG criteria, with modification for treatment-related lymphocytosis.

ORR will be summarized for each treatment arm using a point estimate along with a 95% confidence interval employing the exact binomial method. The proportion of subjects in each response category will also be presented. In the primary analysis of ORR, any subjects not exhibiting a response (eg, CR, CRi, PR, and PRwL) are classified as nonresponders. Additional sensitivity analyses based on other analysis sets or responder definitions may be conducted.

DOR and PFS will be presented for each treatment arm using the Kaplan-Meier method. A 2-sided 95% confidence interval for the median of each of the 2 endpoints will be presented for each treatment arm. Censoring for DOR and PFS will be identical to the method employed for PFS in study IPI-145-07.

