4 ANALYSIS SETS

4.1 All-Treated (AT) Analysis Set

The all-treated (AT) analysis set includes all subjects who receive any amount of study drug (duvelisib or ofatumumab), with treatment group designated according to actual study treatment received. The AT analysis set will be the primary analysis set for efficacy and safety endpoints.

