5.2 Secondary Endpoints

The secondary efficacy endpoints of the study are:

- Treatment-Emergent Adverse Events (TEAEs) and changes in laboratory values
- Duration of Response (DOR), defined as the time from the first documentation of response to the first documentation of progressive disease (PD) or death due to any cause
- Progression-Free Survival (PFS), defined as the time from the first dose of study treatment to the first documentation of PD or death from any cause

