7.2 Efficacy Analyses

ORR, DOR, and PFS will be derived from investigator assessment.

AT analysis set will be the primary analysis set for all efficacy analyses. If analyses are performed on more than one analysis set, the analyses on the AT analysis set will be considered primary. No treatment comparison between the two arms will be performed and only efficacy endpoints for the duvelisib arm will be tabulated and plotted. Data for both treatment arms will be included in data listings.

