10 APPENDICES

A. PFS censoring rule

Censoring of PFS will be performed as detailed in the table below.

Primary PFS Censoring / Event Methodology

Situation	Date of Event or Censoring	Outcome
No adequate baseline disease status assessment	Date of first dose	Censored
No adequate post-baseline disease status assessment unless death occurs prior to first post-baseline assessment	Date of first dose + 1	Censored
No documented progression or death before data cutoff	Date of last adequate disease status assessment	Censored
Documented progression with ≤ 1 missing scheduled disease status assessment before progression	Date of the earliest assessment that results in a finding of unequivocal progression	Event
Death before progression being documented with ≤ 1 missing scheduled disease status assessment before death	Date of death	Event
Documented progression or death following a long gap between adequate disease status assessments (eg, 2 or more consecutive missed scheduled disease status assessments)	Date of last adequate disease status assessment before the gap	Censored
New anticancer treatment or procedure started before documented progression	Date of last adequate disease status assessment prior to new anticancer treatment	Censored

Note: Disease status assessment includes CT scans (chest, abdomen and pelvis), bone marrow aspirate and/or biopsy (may not be required of all subjects at all scheduled disease status assessments), CBC and differential count, focused physical examination, disease related constitutional symptoms for disease assessment, and ECOG performance status. An adequate disease status assessment is any disease status assessment for which the investigator review is able to arrive at a disease status (eg, CR, CRi, PR, PRwL, SD, and PD) per protocol-defined criteria.

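### SAP 7.2.2.2 restricts the PFS Kaplan-Meier analysis to responders, which contradicts the endpoint definition and biases PFS upward

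*SAP*

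**What the plan says.** SAP 5.2 lists PFS as a secondary endpoint, "defined as the time from the first dose of study treatment to the first documentation of PD or death from any cause". SAP 7.2 states that "AT analysis set will be the primary analysis set for all efficacy analyses", and SAP 4.1 puts anyone who took any study drug into that set, whatever their response. Protocol 9.2 agrees: "This analysis set will be the primary analysis set for all efficacy and safety endpoints". Protocol 9.4 says that "DOR and PFS will be presented for each treatment arm using the Kaplan-Meier method" and sets no condition on response.

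SAP 7.2.2.2 departs from this: "PFS will be presented using the Kaplan-Meier method based on all treated subjects with a documentation of response", with response meaning CR, CRi, PR or PRwL by investigator assessment. The preceding section on DOR uses the same sentence: "DOR will be presented using the Kaplan-Meier method based on all treated subjects with a documentation of response". The only sensitivity analysis named in 7.2.2.2 uses the Per-Protocol (PP) set. SAP Section 8, on changes from the protocol, mentions only that ofatumumab results will not be tabulated or plotted.

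**The concern.** Restricting DOR to responders is correct, because its clock starts at response. PFS starts at first dose, so the same restriction conditions the analysis on something that happens later. Protocol 4.3 and 4.4 withdraw subjects from treatment and study at progression. To be counted, a subject must therefore normally stay progression-free until a response is recorded. Early progressions and early deaths, which PFS exists to capture, would be removed.

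The result would describe how long responders remain progression-free, under the label PFS. Two features raise the stakes. Only the duvelisib arm is tabulated and plotted (SAP 7.2 and Section 8), so no second curve would expose the distortion. And SAP 3.5 plans one analysis with a data cutoff timed to the new drug application. The PFS subgroup analyses in SAP 6.5 would have the same problem if run on this population.

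**Working it through.** **Step 1: compare the texts.** The documents give no PFS median, event count or expected ORR, so there is no figure to reproduce. The question is which population the plan prescribes.

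| Place | Population implied for PFS |
|---|---|
| SAP 5.2 (definition) | All treated; starts at first dose, no response needed |
| SAP 7.2 with 4.1 | AT set |
| Protocol 9.2 | AT set |
| Protocol 9.4 | Each arm, no responder restriction |
| SAP Appendix A | Includes subjects never assessed after baseline |
| SAP Section 8 | No change of PFS population declared |
| SAP 7.2.2.2 | Responders only |

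Appendix A has a PFS row headed "No adequate post-baseline disease status assessment unless death occurs prior to first post-baseline assessment". No responder can fall into it, so the table was written for a wider population than 7.2.2.2 allows.

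**Step 2: guaranteed event-free time.** Protocol Table 4 puts the first scheduled on-treatment response assessment at Cycle 4 Day 1. Protocol 4.1 gives a 21-day first cycle and 28-day cycles after it. Time from first dose is 21 + 28 + 28 = 77 days (study day 78), or 77 / 30.4375 = 2.53 months. Until about then a responder-only curve stays near 100%.

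Suppose response carried no prognostic information: constant hazard, and everyone event-free at 77 days equally likely to be a responder. The responder-only median is then M + 2.53, where M is the all-treated median. For M = 6, 9 and 12 months this gives 8.5, 11.5 and 14.5 months.

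**Step 3: illustrative mixture.** Let t = 2.53 months, p = ORR, M_R = responder median and M_N = non-responder median, all medians measured from first dose.

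- Responders: S_R(s) = 1 for s < t, then 0.5^((s − t)/(M_R − t)).
- Non-responders: S_N(s) = 0.5^(s/M_N).
- All treated: S(s) = p·S_R(s) + (1 − p)·S_N(s); the median solves S(s) = 0.5.

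The values of p, M_R and M_N are assumptions, not taken from the documents.

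| p | M_R | M_N | All-treated median | Excess of responder-only median | 6-month PFS, responders | 6-month PFS, all treated |
|---|---|---|---|---|---|---|
| 0.50 | 12 | 3 | 6.2 | 5.8 | 78% | 51% |
| 0.50 | 12 | 5 | 8.0 | 4.0 | 78% | 60% |
| 0.50 | 15 | 3 | 6.8 | 8.2 | 83% | 54% |
| 0.50 | 15 | 5 | 8.8 | 6.2 | 83% | 63% |
| 0.80 | 12 | 3 | 9.6 | 2.4 | 78% | 67% |
| 0.80 | 12 | 5 | 10.3 | 1.7 | 78% | 71% |
| 0.80 | 15 | 3 | 11.5 | 3.5 | 83% | 71% |
| 0.80 | 15 | 5 | 12.3 | 2.7 | 83% | 75% |

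Worked example, first row at 6 months: S_R = 0.5^((6 − 2.53)/(12 − 2.53)) = 0.776; S_N = 0.5^(6/3) = 0.25; S = 0.5 × 0.776 + 0.5 × 0.25 = 0.513.

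A wider grid (p from 0.40 to 0.85, M_R 12 or 18, M_N 3 or 6) gives an excess of 1.0 month (p = 0.85, M_R = 12, M_N = 6) to 12.2 months (p = 0.40, M_R = 18, M_N = 3). The excess was positive in every scenario and shrinks as ORR approaches 100%.

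**The case against.** The strongest reply is that this is a drafting slip. The wording repeats the DOR sentence, SAP 7.2 names the AT set for all efficacy analyses, and Section 8 declares no change, so a programmer might well use all treated subjects. A carry-over error is indeed the likeliest explanation, and the bias arises only if the sentence is followed. But 7.2.2.2 is the specific instruction. It can be read as a subset of AT, exactly as the DOR sentence must be, so 7.2 does not override it. No all-treated PFS analysis is named in that section.

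Several narrower points stand:

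- The Appendix A evidence is one row, with early death as its exception. The same table is applied to DOR, where that row cannot apply either. It supports the reading but weighs less than the definition and the AT statements.
- Whether the PP analysis inherits the restriction is unclear. The PP set is defined by protocol compliance, not response, and 7.2.2.2 does not say.
- Subgroup PFS is run only if sample sizes allow.
- Day 78 is nominal. Cycle windows are ±2 and ±4 days, scans may be done up to 7 days early, and unscheduled assessments count (SAP 6.7), so the lead-in could be shorter.
- PFS is secondary and descriptive, with no test and no comparison between arms. Primary ORR keeps all subjects in the denominator and is unaffected.

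None of these supplies a reason for a responder-only PFS or changes the direction of the bias.

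**Conclusion.** The concern holds. As written, SAP 7.2.2.2 prescribes a PFS population that contradicts the SAP's own endpoint definition and primary analysis set, and Protocol 9.2 and 9.4, without declaring a change. If followed, it overstates PFS. The direction follows from selecting on a later outcome. The size is illustrative: about 1.7 to 8.2 months in the median over ORR 50–80%, responder median 12–15 months and non-responder median 3–5 months, with exponential times and first response at 77 days. This should be corrected before analysis: no error rate or primary result depends on it, but the reported figure would not be the stated endpoint.

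**What to change.** In SAP 7.2.2.2, replace the population with all subjects in the AT analysis set, measured from first dose and censored under Appendix A. Leave the responder restriction in 7.2.2.1 for DOR only. State that the PP and subgroup PFS analyses include all subjects in those sets, whatever their response.

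The cost is one or two sentences of SAP text; no new data or procedures are needed. The reported PFS will be less favourable than a responder-only figure, but it will estimate the defined endpoint. If a responder-only curve is still wanted, it should be labelled as supplementary and not as PFS.

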7.3 Safety Analyses

All safety analyses will be performed using the AT analysis set.

7.3.1 Adverse Events

Adverse events will be coded using MedDRA Version 16.1 or higher. The Grade of the AE will be assessed according to the NCI-CTCAE Version 4.03. If an AE is not included in the NCI-CTCAE Version 4.03, the Grade of the AE will be assessed according to the protocol, Section 8.2.1.2.

AEs will be summarized by MedDRA system organ class (SOC) and preferred term (PT), or PT only. For summary tables by SOC and PT, SOC will be sorted alphabetically and PT will be sorted by decreasing frequency in the duvelisib arm within each SOC. For summary tables by PT only, PT will be sorted by decreasing frequency in the duvelisib arm.

If multiple AEs of the same PT occur within a subject, only the maximum grade observed for this PT will be used in summary of AEs by grade, the subject will be counted only once in the number of subjects for this PT and only once for the number of subjects for the SOC to which this PT belongs.

A treatment-emergent AE (TEAE) is defined as any AE that emerges or worsens in the period from the first dose of study treatment to 30 days after the last dose of study treatment. The onset date of an AE will be compared to the first dose date and the last dose date plus 30 days to determine whether the AE is treatment-emergent or not. If the onset date of an AE is completely or partially missing, refer to [Section 6.2.1](#) for the algorithm to determine whether an AE is treatment emergent.

An overview TEAE summary table will be provided, which will include the number of AEs and the number of subjects with AEs in selected categories. In addition, TEAEs will be summarized for the following categories, and will be tabulated by SOC and PT, unless otherwise specified.

- Treatment-emergent AEs (All Causalities)
- Treatment-emergent AEs (Treatment-Related)
- Treatment-emergent AEs (All Causalities, by maximum grade)
- Treatment-emergent AEs (Treatment-Related, by maximum grade)
- Grade 3 or higher treatment-emergent AEs (All Causalities)
- Grade 3 or higher treatment-emergent AEs (Treatment-Related)
- Treatment-emergent SAE (All Causalities)
- Treatment-emergent SAE (Treatment-Related)
- Treatment-Emergent AEs Resulting in Discontinuation of Study Drug
- Treatment-Emergent AEs Resulting in dose hold or reduction (number of subjects with hold, reduction, hold or reduction will be displayed)
- Treatment-Emergent AEs Resulting in Death
- Treatment-Emergent AEs by PT (All Causalities)
- Grade 3 or higher treatment-emergent AEs by PT (All Causalities)

A by-subject listing of the following AE categories will be presented.

- All AEs (TEAEs will be flagged)
- All SAEs (TEAEs will be flagged)
- Treatment-Emergent AEs Resulting in Discontinuation of Study Drug
- Treatment-Emergent AEs Resulting in Death

Treatment-emergent AEs (All Causalities) and Treatment-emergent AEs (Treatment-Related) will also be tabulated in each subgroup specified in [Section 6.5](#).

7.3.2 Laboratory Data

Laboratory tests will be reported separately for hematology/coagulation, blood chemistry, and urinalysis.

For the purposes of presentation in both tables and listings, the following laboratory test results will be converted to the International System of Units (SI) before presentation: sodium, potassium, chloride, bicarbonate (or CO₂), albumin, total protein, creatinine, blood urea nitrogen(BUN), lipase, amylase, uric acid, calcium, phosphorus, magnesium, glucose, lactate dehydrogenase(LDH), serum ALT, serum AST, total and direct bilirubin, and alkaline phosphatase, red blood cell (RBC) count, hemoglobin, hematocrit, platelets, white blood cell count with 5-part differential performed manually or by flow cytometry (for an absolute neutrophil count [ANC], lymphocyte count, neutrophils, lymphocytes, monocytes, basophils, and eosinophils), prothrombin time(PT), activated partial thromboplastin time(aPTT), international normalized ratio (INR) etc.

If a laboratory test value is reported using a non-numeric qualifier (e.g., less than [$<$] a certain value, or greater than [$>$] a certain value), the given numeric value will be used in the summary statistics, ignoring the non-numeric qualifier.

For laboratory tests with NCI-CTCAE grades, a shift table from baseline grade to the maximum post-baseline grade will be provided. Laboratory tests with bi-directional grades (e.g., Hyperglycemia and Hypoglycemia) will be presented separately for each direction within the shift table.

Listings will be provided for all laboratory test results and for laboratory test results grade 3 and higher. A listing of subjects with ALT or AST $>3xULN$ with simultaneous total bilirubin $>2xULN$ will be presented, where ULN stands for upper limit of normal.

7.3.3 Vital Signs

The actual values of vital sign parameters, including temperature, heart rate, weight and systolic and diastolic blood pressure, will be presented in a by-subject listing.

7.3.4 Electrocardiogram (ECG)

The ECG categories will be summarized for baseline and for each visit. The categories include normal, abnormal, NCS (abnormal but not clinically significant) and abnormal CS (abnormal and clinically significant).

7.3.5 Physical Examination

A full physical examination will be performed during Screening and focused physical examination will be performed every 2 cycles and every 6 cycles starting Cycle 24. A list of abnormal findings will be provided.

7.3.6 Eastern Cooperative Oncology Group (ECOG)

ECOG Performance Status will be assessed during Screening, every 2 cycles and every 6 cycles starting Cycle 24. A listing of all the ECOG performance status will be provided.

7.3.7 Concomitant Medications and Procedures

Please refer to Section 7.1.7 for the definition and summary of concomitant medications.

Concomitant procedures will not be summarized. A by-subject listing will be presented.

7.3.8 Pregnancy

A listing of Serum Pregnancy Test for woman with child-bearing potential will be provided.

8 CHANGES IN PLANNED ANALYSES FROM PROTOCOL

Due to the very small number of subjects (n=8) in the ofatumab treatment arm only results for the duvelisib treatment arm will be tabulated and plotted. Subjects from both treatment arms will be present in the data listings.

10 APPENDICES

A. PFS censoring rule

Censoring of PFS will be performed as detailed in the table below.

Primary PFS Censoring / Event Methodology

Situation	Date of Event or Censoring	Outcome
No adequate baseline disease status assessment	Date of first dose	Censored
No adequate post-baseline disease status assessment unless death occurs prior to first post-baseline assessment	Date of first dose + 1	Censored
No documented progression or death before data cutoff	Date of last adequate disease status assessment	Censored
Documented progression with ≤ 1 missing scheduled disease status assessment before progression	Date of the earliest assessment that results in a finding of unequivocal progression	Event
Death before progression being documented with ≤ 1 missing scheduled disease status assessment before death	Date of death	Event
Documented progression or death following a long gap between adequate disease status assessments (eg, 2 or more consecutive missed scheduled disease status assessments)	Date of last adequate disease status assessment before the gap	Censored
New anticancer treatment or procedure started before documented progression	Date of last adequate disease status assessment prior to new anticancer treatment	Censored

Note: Disease status assessment includes CT scans (chest, abdomen and pelvis), bone marrow aspirate and/or biopsy (may not be required of all subjects at all scheduled disease status assessments), CBC and differential count, focused physical examination, disease related constitutional symptoms for disease assessment, and ECOG performance status. An adequate disease status assessment is any disease status assessment for which the investigator review is able to arrive at a disease status (eg, CR, CRi, PR, PRwL, SD, and PD) per protocol-defined criteria.
